An adequate post-baseline assessment is defined as an assessment where a response of sCR, CR, VGPR, PR, MR, SD, Relapse or PD can be determined based on IMWG response criteria for multiple myeloma. Subjects with no baseline disease assessment (including subjects with an inadequate baseline assessment) or with no adequate post-baseline disease assessments within 46 days for cohorts with 21 day cycles and 60 days for cohorts with 28 day cycles after the date of first dose will be censored on the date of first dose, unless the subject dies within 46 days for cohorts with 21 day cycles and 60 days for cohorts with 28 day cycles of the date of the first dose, in which case, death will be an event on date of death. Subjects will be considered to have progressive disease if they meet the criteria for progression by a variable that was not considered measurable at baseline.

Events and censoring rules are summarized in Table 4.

Table 4. Progression Free Survival

Situation	Date of Progression/Censoring¹	Outcome
Inadequate baseline assessment	First dosing date in Cycle 1 (or Cycle 0 for priming cohorts)	Censored
No on-study assessments	First dosing date in Cycle 1 (or Cycle 0 for priming cohorts)	Censored
Alive, on treatment ² and no Progression	Date of last objective tumor assessment ³	Censored
New anti-cancer therapy	Date of last adequate disease assessment that documented no progression prior to new anti-cancer therapy	Censored
Progression Documented on or between scheduled tumor assessments prior to treatment discontinuation ²	Date of first objective tumor assessment showing objective progression	Progressed (Event)
Withdrawal of consent prior and refusal to follow-up	Date of last objective tumor assessment prior to	Censored

	discontinuation ²	
Treatment discontinuation for undocumented progression, toxicity or other reason	Date of last objective tumor assessment prior to discontinuation ²	Censored
Death prior to first planned tumor assessment	Date of death	Death (Event)
Death without objective progression prior to treatment discontinuation ²	Date of death	Death (Event)
Death or progression after 2 or more missed tumor assessments ⁴	Date of last objective tumor assessment prior to the event	Censored
Lost to follow-up	Date of last objective tumor assessment ³	Censored

1. For date of censorship, if a tumor assessment takes place over a number of days (e.g., superficial lesions one day, scans another), the last date is used as the assessment date.

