2. or within 28 days of discontinuation of treatment.
3. Date of last adequate disease assessment that documented no progression
4. This would be 46 days for cohorts with 21 day cycles and 60 days for cohorts with 28 day cycles

Reasons for censoring should be summarized according to the categories in Table 5.

Table 5. PFS Censoring Reasons and Hierarchy

Hierarchy	Condition	Censoring Reason
1	No adequate baseline assessment	No adequate baseline assessment
2	Start of new anti-cancer therapy before event.	Start of new anti-cancer therapy
3	Event after 2 or more missed tumor assessments/start date	Event after missing assessments ^a
4	No event and [withdrawal of consent date \geq date of first dose OR End of study (EOS) = Subject refused further FU]	Withdrawal of consent
5	No event and lost to follow-up in any disposition page	Lost to follow-up
6	No event and [EOS present OR disposition page for any EPOCH after screening says subject will not continue into any subsequent phase of the study] and no adequate post-baseline disease assessment	No adequate post-baseline disease assessment
7	No event and none of the conditions in the prior hierarchy are met	Ongoing without an event

^a 2 or more missed tumor assessment.

Disease Assessment Date: The Date of Disease Assessment at each nominal timepoint as provided by the investigator on the IMWG response CRF page will be utilized for the respective analyses.

Adequate Baseline Disease Assessment: Adequate baseline is defined using the following criteria:

- All baseline disease assessments (IMWG responses) must be within 28 days prior to and including the date of first dose;
- Measurable disease based on IMWG criteria as defined by at least 1 of the following:
 - Serum M-protein ≥ 0.5 g/dL by SPEP;
 - Urinary M-protein excretion ≥ 200 mg/24 hours by UPEP;
 - Serum immunoglobulin FLC > 10 mg/dL (> 100 mg/L) AND abnormal serum immunoglobulin kappa to lambda FLC ratio (< 0.26 or > 1.65).

Adequate Post-baseline Disease Assessment: An adequate disease assessment is defined as an assessment where a time-point response of sCR, CR, VGPR, PR, minimal response (MR), Stable Disease (SD) or PD has been provided.

Timepoints where the response is not evaluable or no assessment was performed will not be used for determining the censoring date for time-to-event endpoints including PFS, DOR and DOCR.

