8.2.2.6. Duration of Response (DoR)

DoR is defined, for participants with an objective response per IMWG criteria, as the time from the first documentation of objective response that is subsequently confirmed, until PD per IMWG criteria, or death due to any cause, whichever occurs first. It will be calculated as follows:

$$\text{DoR (months)} = [\text{date of event or censoring} - \text{first date of objective response} + 1] / 30.4375$$

The censoring rules for DoR are as described for PFS in Section 8.2.2.1, except that participants will not be censored for inadequate baseline assessment or for no adequate post-baseline assessment, as only participants with an objective response are included in the analysis of DoR.

If at least 3 participants achieve an objective response and subsequently have an event, DoR will be estimated using the same Kaplan-Meier method as described for PFS in Section 8.2.2.1 and displayed graphically where appropriate. Otherwise, only listings will be provided.

The DoR rate at 3, 6, 9, 12 and 18 months (and in subsequent 6-month increments while there are participants still at risk) will be estimated with corresponding two-sided 95% CIs.

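### SAP 8.2.2.1 censors PFS at first dose when the first adequate assessment comes after 46/60 days, even if the patient later responds and progresses; its own Tables 4 and 5 do not

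*SAP*

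**What the plan says.** SAP 8.2.2.1 states the rule for early censoring of PFS in two ways.

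- **Running text.** The trigger is an inadequate or absent baseline, or "no adequate post-baseline disease assessments within 46 days for cohorts with 21 day cycles and 60 days for cohorts with 28 day cycles". The consequence is that such patients, "after the date of first dose will be censored on the date of first dose, unless the subject dies within 46 days for cohorts with" 21-day cycles (60 days for 28-day cycles), contribute no follow-up. A death inside the window counts as an event.
- **Table 4**, which the text presents as its summary. First-dose censoring applies to an "inadequate baseline assessment" and to "No on-study assessments". Neither row has a time limit. Documented progression is an event on the "Date of first objective tumor assessment showing objective progression", whenever the first assessment took place. A separate row, "Death or progression after 2 or more missed tumor assessments", censors at the last assessment before the event. Footnote 4 equates two missed assessments with 46 or 60 days.
- **Table 5.** Row 6 needs no event, a patient who is off study, and "no adequate post-baseline disease assessment", again without a window. Row 3 lets the gap be counted from the start date.
- **Opening paragraphs of 8.2.2.1.** PD or death after at most one missing assessment is an event. Only patients with no event, or with an event after two or more missed assessments, are sent to Table 4 for censoring.

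For duration of response, SAP 8.2.2.6 says that "participants will not be censored for inadequate baseline assessment or for no adequate post-baseline assessment". DoSD (SAP 8.2.2.10) adopts the PFS censoring rules. DoCR (SAP 8.2.2.7) is said first to follow PFS and then to follow DoR.

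**The concern.** The running text has no exception for a patient whose first adequate assessment is late but who is followed normally afterwards. Such a patient is known to be progression-free beyond the window, yet is removed on day 1. The tables keep the same patient. A programmer must choose, and the choice changes the PFS record from an event at many months to a one-day censored time.

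Three outputs could then disagree for one patient: a confirmed response with a full DoR, a PFS with no follow-up, and a DoSD that ends before it starts. A patient still responding would be censored on day 1 by the text but carry the Table 5 row 7 reason, ongoing with no event.

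**Working it through.** **The window.** The SAP gives no derivation. The figures reproduce as two cycles with 2 days' allowance each: 2 × (21 + 2) = 46 and 2 × (28 + 2) = 60. The allowance is my inference.

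**Text against tables.** Hypothetical patients in a 28-day cohort with an adequate baseline. Day 1 is first dose.

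| Patient | Running text | Tables 4 and 5 |
|---|---|---|
| First adequate assessment day 64 (PR), then regular, PD day 330 | Censored day 1 | Event day 330 |
| Same, still responding at day 316 | Censored day 1 | Censored day 316 |
| First assessment day 64 is PD | Censored day 1 | Censored day 1 (gap from start date) |
| No assessment, alive | Censored day 1 | Censored day 1 |
| No assessment, death day 40 | Event day 40 | Event day 40 |
| No assessment, death day 80 | Censored day 1 | Censored day 1 |
| Regular assessments, PD day 330 | Event day 330 | Event day 330 |

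The two rules part only in the first two rows.

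**Size for the first patient**, dividing by 30.4375 days per month:

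- PFS, tables: 330 / 30.4375 = 10.84 months, event.
- PFS, text: 1 / 30.4375 = 0.03 months, censored.
- DoR: (330 − 64 + 1) / 30.4375 = 8.77 months, event.
- DoSD under the text, if the day-64 record were SD: 1 − 64 + 1 = −62 days. The floor of 1 day in SAP 8.2.2.10 is written only for patients without an adequate baseline, so it does not apply.

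**How it can arise.** The Schedules of Activities place the serum and urine tests on Day 1 of each cycle.

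- Unprimed: C3D1 falls 42 days (21-day cycles) or 56 days (28-day cycles) after first dose. A non-evaluable C2D1 plus a delay of C3D1 by more than 4 days passes the window.
- Primed: C1D1, C2D1 and C3D1 fall 7, 35 and 63 days after first dose. Both C1D1 and C2D1 must fail to give an adequate status.

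**Effect on a cohort.** Protocol 1.2.3.1 reports 15 patients in Part 2A, 9 in Part 1D and 4 in Part 1C. One affected patient is 1/15 = 6.7%, 1/9 = 11.1% or 1/4 = 25% of the cohort.

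For a larger group, take exponential PFS with the reported median of 10.4 months (Protocol 1.2.3.2). Assume that a share p of patients progression-free at 60 days is censored on day 1, and that they are otherwise like the rest. The documents give no value for p.

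- S(60 days) = exp(−ln 2 × 60 / (10.4 × 30.4375)) = 0.877.
- Under the text it becomes 1 − 0.123 / (1 − 0.877p). For p = 5%, 10%, 20% this is 0.871, 0.865, 0.851.
- The median solves (1 − p)S(t) / (1 − 0.877p) = 0.5, giving 10.3, 10.2 and 9.9 months.

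The reported 95% CI for the median is 4.7 to 15.2 months. In simulated cohorts of 20 on the same model, followed for 24 months, 1 to 4 affected patients lowered the mean number of events from about 16 to 15.2, 14.5, 13.6 and 12.9. The typical Kaplan-Meier median moved by −0.65 to +0.55 months, with no consistent direction.

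**The case against.** The strongest reply is that the SAP shows what it means elsewhere. DoR drops this censoring because only responders enter that analysis, and that reason works only if the category means no assessment at all. The DoSD floor covers only an inadequate baseline, which suggests that the authors saw no other route by which an assessed patient is censored at first dose. Both tables agree, and the text defers to Table 4 as its summary. This is good evidence of intent, but it does not change what the sentence instructs.

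The reply does dispose of several stronger readings that a reader might infer:

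- *That every patient without an early assessment is censored.* Deaths inside the window are events.
- *That the tables censor at first dose only when nothing was assessed.* They also do so for an inadequate baseline, and, by the gap rule with Table 5 row 3, when the first late record is PD or death.
- *That the window is wrong for primed cohorts because C3D1 lies beyond 60 days.* Schedule of Activities B has serum and urine tests at C1D1 and C2D1, so a primed patient has two scheduled laboratory assessments inside the window, as an unprimed patient does. SD is enough to make one adequate. The 48 of 101 patients in Parts 1.1, 2A, 1C and 1D (20 + 15 + 4 + 9) are the total enrolled in those parts, not a count of those affected.
- *That reported PFS is materially biased downward.* This needs a programmer to follow the one sentence over both tables, and an affected share that the documents do not give.

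It also stands that PFS is a secondary endpoint in both parts, without formal hypothesis testing, and that ORR and DoR are untouched.

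**Conclusion.** The concern holds as a conflict within SAP 8.2.2.1. As written, the text and the tables give different PFS results for a patient first adequately assessed after 46/60 days and then followed, and the text's result contradicts that patient's own DoR. DoSD inherits the fault. DoCR does too if its first statement, that it follows PFS, is applied.

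For an individual the difference can be the whole follow-up (10.84 months against 0.03 in the example). Across a cohort it is probably small: under the assumed model, up to 0.026 in S(60 days) and about half a month in the median at p = 20%. Those figures rest on an exponential curve, an assumed share and non-informative lateness. The number actually affected cannot be determined from the documents. In cohorts of 4 to 15, a single case is visible.

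**What to change.** In SAP 8.2.2.1, restrict first-dose censoring on post-baseline grounds to two groups: patients with no adequate post-baseline assessment at any time, and patients whose first record, more than 46/60 days after first dose, is PD or death. Keep death inside the window as an event and leave the baseline rule unchanged. Treat everyone else as Table 4 does: later events count, and patients without an event are censored at the last adequate assessment.

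Carry the same rule into DoSD, where the negative values from late assessment then disappear without another patch. State one censoring rule for DoCR in place of the present two. The start and length of the window need no change.

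The cost is a few sentences of SAP text and a small program change, before database lock. No new data are needed.

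### SAP Table 4 stops counting progression and most deaths 28 days after treatment ends, but the text of 8.2.2.1 that it summarises has no such limit, and Part 2's primary DoR inherits the conflict

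*SAP*

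**What the plan says.** SAP 8.2.2.1 gives the PFS rules twice, in text and in a table.

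- **Text.** PD or death is an event if no more than one assessment was missed before it. A single PD recorded after treatment has ended is listed as a progression, with no day limit. The grounds for censoring are: no event, an event after two or more missed assessments, new anti-cancer therapy, and an inadequate baseline or early post-baseline assessment.
- **Table 4.** It is introduced with "Events and censoring rules are summarized in Table 4". Its event rows are "Progression Documented on or between scheduled tumor assessments prior to treatment discontinuation", "Death without objective progression prior to treatment discontinuation" and "Death prior to first planned tumor assessment". The first two carry footnote 2, "or within 28 days of discontinuation of treatment". The third has no treatment limit. Patients with "Treatment discontinuation for undocumented progression, toxicity or other reason" are censored at the last assessment before discontinuation, again with footnote 2.
- **Footnote 4** defines two or more missed assessments: "This would be 46 days for cohorts with 21 day cycles and 60 days for cohorts with 28 day cycles".
- **Table 5** lists the censoring reasons. None refers to stopping treatment. The last row is the catch-all "No event and none of the conditions in the prior hierarchy are met".

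SAP 8.2.2.6, 8.2.2.7 and 8.2.2.10 take these rules over for DoR, DoCR and DoSD. SAP 2.2.2 makes DoR a Part 2 primary endpoint with ORR. Protocol 9.4 defines DoR up to progression or death from any cause, with no reference to treatment.

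**The concern.** A table offered as a summary is narrower than the text it summarises. A PD more than 28 days after treatment ends, or a death that late once the first planned assessment has passed, can be an event under the text but has no event row in Table 4. Two programmers working from the same SAP could each defend a different primary DoR.

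The affected data will exist. Protocol 7.2 has standard-of-care response assessments reported after treatment until progression, new therapy or the end of follow-up, and SAP 8.2.2.2 expects survival status regardless of discontinuation. If Table 4 is applied, Table 5 cannot describe the result: such a patient falls into the catch-all row and is labelled as still event-free, although an event is on record.

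**Working it through.** **1. The rules side by side, for a patient who stops without PD and starts no new therapy**

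| Later event | Text | Table 4 with footnote 2 |
|---|---|---|
| PD or death up to 28 days after stopping | Event | Event |
| PD or death after day 28, no more than one missed assessment | Event | No event row, so censored |
| PD or death after two or more missed assessments | Censored | Censored |
| Death before the first planned assessment | Event | Event |

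The missed-assessment rule does not explain the cut-off: 2×21+4 = 46 and 2×28+4 = 60 days, and both exceed 28.

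**2. Two patients in a 28-day-cycle cohort**

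- A responder is last assessed on the day treatment stops, starts no new therapy and dies 45 days later. Because 45 ≤ 60, the text counts an event. Because 45 > 28, Table 4 censors.
- Response on day 0; last assessment before stopping for toxicity on day 224; assessments continue every 28 days; PD on day 300. Text: event, DoR = (300+1)/30.4375 = 9.9 months. Table 4: censored at (224+1)/30.4375 = 7.4 months, or up to about 28 days later if an assessment falls inside the window.

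**3. Size**

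The SAP states no figure to reproduce. The documents give neither the rate of stopping without PD nor the spacing of off-treatment assessments, so the size was simulated.

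Assumptions: on-treatment median DoR 12 months (hazard ln2/12 per month); 10, 30 or 40% stopping without PD by month 12; hazard 1, 2 or 3 times as high after stopping; median 3 or 6 months to new therapy; 20% of events are deaths; 28-day assessments on treatment and one at stopping; 24-month cut-off; 60-day gap rule kept as the text has it. That gives 3×3×2 = 18 scenarios per off-treatment spacing.

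| Off-treatment assessments | Share of the text's events that Table 4 drops |
|---|---|
| Every 28-56 days | about 2-26% |
| Every 91 days | 0.3-4% |
| None | 0.1-1.6% |

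Two scenarios for the 12-month DoR rate:

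- 30% stopping, hazard ratio 2, new-therapy median 6 months, 28-day spacing: Table 4 48.8%, text 47.0%, true 45.5%. Table 4 drops 14.5% of events.
- 40% stopping, hazard ratio 1, new-therapy median 6 months, 91-day spacing: Table 4 49.0%, text 53.1%, true 49.7%. Without the 60-day rule after treatment: 50.0%.

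Part 2A enrolled 15 (Protocol 1.2.3.1). At the 63.4% response rate of the 41 patients in Protocol 1.2.3.2, used here as an assumption, that is 0.634×15 = 9.5 responders. A loss of 14.5% is then about one event (0.98).

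**The case against.** **The 28-day rule may be intended.** It matches the follow-up visit 28-35 days after treatment (Protocol 6.3), after which response assessments are only standard of care, and the text sends some patients to Table 4 for censoring. Intent cannot be settled from the documents. But the text refers to Table 4 only patients without an event or with an event after two or more missed assessments, not patients whose event it has just counted. If the rule is intended, the text and Table 5 still need to change.

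**The discontinuation row may cover only patients with no later event.** That reading is open, and the row alone would not prove a conflict. The conflict lies in the two event rows, which carry the same limit.

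**The effect is small.** This largely stands. SAP 8.2.2 plans no hypothesis test. With 9.5 responders the standard error of a 12-month rate near 50% is about √(0.5×0.5/9.5) = 16 points.

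Three stronger readings are tempting, and the documents support none of them:

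- *That the larger loss applies whatever the assessment spacing.* It would at 91 days only if the missed-assessment rule were switched off after treatment. Neither the text nor Table 4 does that.
- *That the 46/60-day rule cannot operate off treatment and must be dropped there.* It is a fixed day count and can be programmed without a visit schedule. Whether it suits standard-of-care spacing is a judgement, and dropping it in the main analysis would depart from the text and from Table 5's third row.
- *That Table 4 inflates DoR.* The direction depends on the hazard after stopping and on spacing. At 91 days the text's rule lay further from the true 12-month rate than Table 4 in all 18 scenarios.

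**Conclusion.** The conflict is real and can be read from the page without any simulation. Table 4 with footnote 2 has no event row for PD, or for death after the first planned assessment, more than 28 days after treatment ends. The text, Table 5 and the protocol's DoR definition contain no such limit. Part 2's primary DoR is affected, as are PFS, DoCR and DoSD. ORR and OS are not.

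The modelled loss, from a fraction of 1% up to about a quarter of events, rests on assumed stopping rates, hazards and spacing, so it shows a range and is not a forecast. It bears on descriptive estimates in small cohorts. It should be corrected because it touches a primary endpoint and costs little, not because a conclusion is known to be wrong.

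**What to change.** Align Table 4 with the text, Table 5 and Protocol 9.4:

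1. Remove the treatment-discontinuation condition and footnote 2 from the progression and death event rows.
2. Limit the row for patients alive on treatment and the discontinuation row to patients with no later qualifying event. Censor them at the last adequate assessment documenting no progression, on or off treatment.
3. Keep new-therapy censoring and the 46/60-day missed-assessment rule as the text has them. Apply the same rules to DoR, DoCR and DoSD.
4. For DoR and PFS, report two sensitivity analyses: (a) the present 28-day rule; (b) the 46/60-day rule not applied after treatment discontinuation. Analysis (b) is needed because with sparse standard-of-care assessments the text's rule keeps event-free follow-up while censoring the PD that ends it.

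If the sponsor wants the 28-day rule as primary, it should instead be written into 8.2.2.1, given its own reason in Table 5, and identified as a difference from the protocol, as SAP section 2 promises for substantial differences.

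Cost: edits to Table 4, light reprogramming before database lock and two extra outputs. The data are already collected. DoR and PFS estimates may move either way. Because Protocol 1.2.3.2 already reports DoR from a June 2022 cutoff (median 11.6 months), the change should be disclosed in the CSR.

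### SAP Table 5 has no PFS censoring reason for treatment discontinuation or for end of study, so these patients can be reported as ongoing

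*SAP*

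**What the plan says.** SAP 8.2.2.1 handles PFS censoring in two tables. Table 4 sets the date and outcome for each situation. Table 5 sets how the reasons are reported: "Reasons for censoring should be summarized according to the categories in Table 5".

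Table 4 keeps two kinds of event-free patient apart. One row is for the patient who is "Alive, on treatment" and has not progressed. Another is "Treatment discontinuation for undocumented progression, toxicity or other reason", censored at the last objective assessment before discontinuation, a limit that a footnote widens with "or within 28 days of discontinuation of treatment".

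Table 5 is a hierarchy of seven rows. In short, they are:

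1. no adequate baseline;
2. new anti-cancer therapy;
3. event after two or more missed assessments;
4. consent withdrawn, or "End of study (EOS) = Subject refused further FU";
5. lost to follow-up;
6. end of study (EOS) present, or a disposition page stating that the "subject will not continue into any subsequent phase of the study] and no adequate post-baseline disease assessment";
7. "No event and none of the conditions in the prior hierarchy are met", labelled as ongoing without an event.

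SAP 8.2.2.6 says: "The censoring rules for DoR are as described for PFS in Section 8.2.2.1", with exceptions for inadequate baseline and for no adequate post-baseline assessment. SAP 8.2.3.3 separately tabulates and lists discontinuation from treatment and from study, with reasons.

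**The concern.** A censoring-reason table lets the reader judge whether follow-up stopped for administrative reasons or for reasons that may be related to prognosis. A patient still being followed at the data cut-off is the administrative case. A patient who stopped for toxicity, or for progression that was never documented, may be informatively censored. Table 4 draws this distinction and Table 5 drops it. The row that receives both kinds of patient carries the reassuring label. Patients who are no longer in the study at all can receive the same label.

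**Working it through.** No sample size, power or event count is involved. The check applies the Table 5 hierarchy in order, first match wins, to the situations that Table 4 and Protocol 6.6 foresee. Adequate baseline is assumed throughout, and no new therapy unless stated.

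| Patient without a PFS event | Row reached |
|---|---|
| On treatment, no progression | 7 |
| Off treatment for toxicity, adequate post-baseline assessment, still in follow-up | 7 |
| Off treatment for undocumented progression, adequate post-baseline assessment, still in follow-up | 7 |
| Off treatment for toxicity, disposition says will not continue, adequate post-baseline assessment | 7 |
| EOS present (completed or sponsor termination), adequate post-baseline assessment | 7 |
| Off treatment for toxicity, will not continue, no adequate post-baseline assessment | 6 |
| Off treatment for toxicity, then new therapy | 2 |
| Off treatment for toxicity, then consent withdrawn | 4 |
| Off treatment for toxicity, then lost to follow-up | 5 |

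The first five lines share one label, although they describe patients on treatment, off treatment and off study. The cause lies in the conditions of rows 4 and 6. EOS counts in row 4 only when the reason is refusal of further follow-up, and in row 6 only when there is also no adequate post-baseline assessment. Once a patient has one adequate post-baseline assessment and avoids rows 1 to 5, neither EOS nor a will-not-continue entry can keep that patient out of row 7.

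Protocol 6.6 gives five reasons for leaving study follow-up. Refusal maps to row 4 and loss to follow-up to row 5. Death is normally a PFS event, or row 3 if it follows missed assessments. Completed follow-up and termination by the sponsor have no row of their own.

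For treatment discontinuation, the two tables compare as follows. Table 4 lets the discontinuation decide where the patient's PFS time stops: the last assessment before it, or within 28 days of it. Table 5 then reports the reason for that stop as ongoing, which is not why Table 4 stopped the clock.

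**The case against.** The strongest reply is that this concerns a label and nothing else. Table 4 fixes every date and outcome, so no PFS median, rate or confidence interval moves. The SAP describes its summaries as non-inferential (8.1) and plans no formal efficacy testing (8.2.2). That stands in full.

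Second, the missing information is reported elsewhere. SAP 8.2.3.3 tabulates and lists reasons for stopping treatment and study in the Safety Analysis Set, which, like the mITT set used for PFS, requires at least one dose. This stands in part: those reasons are not linked to PFS censoring status, so the summary tables do not show how many censored patients stopped for toxicity or undocumented progression.

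Third, ongoing need not mean on treatment. Protocol 7.2 has patients who stop without progression, and who remain in follow-up, continue to have standard-of-care disease assessments reported. Such a patient can fairly be called ongoing in follow-up. This stands, but it cannot extend to patients with EOS present or a will-not-continue entry.

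Some stronger readings are tempting, and the documents do not support them:

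- **Every discontinued patient is mislabelled.** Rows 1 to 6 catch some, and those still in disease follow-up are arguably described correctly. SAP 8.2.2.1 also counts as an event a single PD at the last assessment followed by permanent discontinuation, and treats clinical relapse as PD, so some who stop for deterioration are not censored.
- **At the final analysis, everyone in row 7 is mislabelled.** Protocol 3.1 allows treatment up to about 30 months after the last patient's first dose, so a patient may be on treatment and event-free when the study closes. The SAP introduction also allows interim reports, when patients really are ongoing.
- **The fault reaches the Part 2 primary endpoint.** The DoR section imports the PFS censoring rules, but Table 5 is stated for PFS reasons. SAP 8.2.2 asks only for the number and percentage of events and censorings for DoR. Use of the Table 5 labels there is an inference.

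**Conclusion.** The point holds as a fault in one reporting rule. Followed as written, SAP Table 5 gives a wrong category to patients who have left the study with an adequate post-baseline assessment and meet none of rows 1 to 5. For patients censored under Table 4's discontinuation row who meet none of rows 1 to 6, it conceals the reason for censoring.

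The size cannot be stated from the documents. They do not say how many patients stopped without documented progression, or how many left the study event-free, so any percentage would be a guess. The effect on censoring dates and Kaplan-Meier estimates is nil.

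The conclusion assumes that Table 5 is applied literally and in the order given. It is worth correcting because the label makes possibly informative censoring look administrative, and the separate disposition table only partly repairs that.

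**What to change.** Insert two rows above row 7 of SAP Table 5:

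- *Treatment discontinued without documented progression*, split into undocumented progression, toxicity and other, for patients censored under the matching Table 4 row.
- *Study ended without an event*, for completed follow-up or sponsor termination. State that treatment stopped only because the sponsor closed the study is counted here and not under other.

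Limit row 7 to patients still on treatment or in disease follow-up at the data cut-off. State whether the same reasons are used for DoR, DoCR and DoSD.

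The cost is a few extra table rows and minor programming. The disposition data are already collected for the tables in SAP 8.2.3.3, and no censoring date or estimate needs to be recomputed.
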